## B. Exposure definition

The primary exposure of interest is new (incident) initiation of systemic DEX. DEX exposure is defined with procedure codes (current procedural terminology, CPT-4/healthcare common procedure coding system, HCPCS [*CMS 2020(b)*]), hospital charge codes for the corresponding text strings (e.g., 'dexamethasone', 'decadron'), and drug names referenced from national drug codes (NDC), where there is an absence of evidence of a non-systemic route of administration (e.g., ciprofloxacin 0.3%/dexamethasone 0.1% ear drops are excluded). All available data types with treatment-specific information are used for assessment of DEX exposures, including medical claims, pharmacy claims, and chargemaster records. DEX use is considered "new" if the patient had no record of systemic DEX dispensing or remaining outpatient pharmacy supply during the 90-day *Treatment Washout Window* prior to the cohort entry and up until 1 day prior to treatment index (Day 0, hospital admission date).

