
Pre-admission Covariates (Day -21 to Day -1)
	
COVID-19 symptoms and HCRU prior to the admission date.
	
 
- COVID-19 symptoms: pre-admission COVID-19 symptoms
 
- HCRU: Inpatient hospitalization, emergency room encounter
 

Admission Covariates (Day 0; CED)
	
Demographics, hospital facility characteristics, and COVID-19 severity on the admission date.
	
 
- Hospital and admitting characteristics: Hospital setting type, hospital teaching status, hospital number of beds, admission source, emergency room encounter, ambulance encounter, admission type
 
- COVID-19 severity at admission: mWHO severity categorization on the admission date
 

Pre-treatment Covariates (Day 0 to Day T, inclusive)
	
Treatments administered prior to or concurrent with treatment index date, pre-treatment clinical status, and time from admission to treatment.
	
 
- Pre-treatment COVID-19 status: Highest recorded mWHO severity
 
- Pre-treatment utilization characteristics: Number of days hospitalized, number of days with critical/ICU care, in ICU at treatment index, number of unique department codes, number of unique procedure codes
 
- Demographics: Month of treatment index, age, sex, insurance type, US region
 

*\*Smoking/tobacco use may be under-reported [see section VIII. Limitations for additional detail]*

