3	Confirm baseline confounder balance	We will confirm that the distributions of all potential confounders are balanced for DEX+ vs. referent. Covariate balance will be defined as absolute standardized differences (ASDs) $\leq 0.10$ [Austin 2009].  Although variables with balance prior to PS matching may be removed from the PS model, balance of these variables will still be confirmed after PS matching.  If there is a variable with a small residual imbalance ( $0.10 \leq ASD \leq 0.20$ ), balance may be deemed acceptable if the variable does not predict the outcome among the referent group (defined as an ASD $< 0.10$ when comparing the risk of the outcome in those with the variable vs. those without it). Evaluation of imbalance in outcome prediction will only be conducted once at the end of the diagnostic phase if all other diagnostic criteria are met.	
4	Confirm models are not overfit	We will confirm that all models contain approximately 12 exposed subjects or more per covariate	

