- **Unstructured inpatient medication data:** Unlike outpatient pharmacy data, inpatient medication data in the HealthVerity data is largely captured via vendor charge code fields (e.g., ‘DEXAMETHASONE 4 MG OR TABS’) in addition to medical procedural claims such as HCPCS for medication administration (e.g., J1095 - INJECTION, DEXAMETHASONE ACETATE, PER 8 MG) that have non-standardized free-text descriptions rather than standardized fields (e.g., NDC codes). Therefore, text search strings will be used to query the data when procedure codes are not available. For this reason, it is possible that some of the patients included using our primary definition for systemic DEX may have non-systematic use that was not excluded due to a lack of indication in the search string. However, we assume this to be rare. Our team has developed a series of search string algorithms to minimize the potential for error and will incorporate additional manual review for key measures.
- **Potential for residual confounding:** Although best practices will be applied to control for confounding, the potential for residual confounding still exists in observational cohort analyses. We will apply RSS to match on time-related biases, which are assumed to be strong given the evolving healthcare landscape of the COVID-19 pandemic that will include other matching factors of importance (i.e., time since admission, age, sex, and comorbidity score). Furthermore, we will use PS matching on top of RSS matching and will not conduct inferential comparative analyses until we have satisfied the balancing criteria specified in the diagnostic checklist. Finally, a number of *a priori* specified sensitivity analyses will evaluate the robustness of our findings. If warranted, post hoc sensitivity analyses may also be conducted to evaluate the potential impact of unmeasured confounding. Although we recognize that factors causing residual confounding may manifest after index, this study does not account for changes in disease severity and other COVID-19 treatment received after index date to avoid additional potential bias that may be induced by conditioning on mediating variables in the causal pathway, or on colliders.

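### The candidate count of unique procedure codes runs through Day T with no exclusion stated, so in DEX+ patients it can include the code that defines exposure

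*Protocol*

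**What the plan says.** - **Covariate.** Protocol section V.F, Table 3, lists "number of unique department codes, number of unique procedure codes" among the pre-treatment utilization characteristics. The window is "Day 0 to Day T, inclusive". Table 3 describes this block as covering "Treatments administered prior to or concurrent with treatment index date", so care given on the index day is captured on purpose.
- **Exposure.** Section V.B states that "DEX exposure is defined with procedure codes" (CPT-4/HCPCS), together with "hospital charge codes for the corresponding text strings" and drug names taken from NDC codes. Department codes are not part of the definition.
- **Example code.** Section VIII.A gives "J1095 - INJECTION, DEXAMETHASONE ACETATE, PER 8 MG" as a HCPCS entry for the drug. It also says that "inpatient medication data in the HealthVerity data is largely captured via vendor charge code fields", with HCPCS as an additional source.
- **Referents.** Under section V.C.2, a CSI- referent has used no corticosteroid of interest as of the matched user's index date and takes that date as Day T. A DEX- referent has used no dexamethasone by then.
- **Use of the covariate.** Section V.F makes the Table 3 variables candidates for the PS and says that some may be left out. Section VI.B, Table 4, row 3 applies to all potential confounders: "Covariate balance will be defined as absolute standardized differences" of at most 0.10. Section VI.C allows Cox adjustment for residual imbalance of 0.10 to 0.15.

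**The concern.** For a DEX+ patient, Day T is the day dexamethasone starts. If that start is recorded by a procedure code, the code falls inside the window of the procedure-code count. The count is meant to measure intensity of care before treatment, but in one arm it can also record the treatment.

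Two patients with the same care before treatment would then show different counts, and matching on the recorded count would pair the DEX+ patient with a referent who had one more other procedure. The balance table cannot reveal this, because it uses the same recorded count. If more procedures mark sicker patients, the referents are tilted toward worse prognosis and the hazard ratio toward benefit.

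The index-day medications in Table 3 do not share the problem: they are a named list without the corticosteroids of interest. The code counts carry no such restriction.

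**Working it through.** The protocol gives no figure for this artefact, so there is none to reproduce. The check has three steps.

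**1. Does the overlap exist as written?** The count includes Day T (Table 3). Dexamethasone on Day T may be recorded as a CPT/HCPCS code (V.B, with an example in VIII.A). No exclusion is stated. By comparison:
- **CSI-:** the referent can have no corticosteroid code in the window, so the asymmetry is complete.
- **DEX-:** the same, except for a referent who starts another corticosteroid of interest.
- **MPRED+:** each arm can add the code for its own drug, so the comparison is roughly symmetric.

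**2. Size before matching.** Let f be the share of DEX+ patients who gain one unique code from dexamethasone, and SD the standard deviation of the count, equal in both arms. With identical true counts,

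ASD = f / √[(SD² + SD² + f(1 − f)) / 2] ≈ f / SD.

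Example: f = 0.5 and SD = 3 give 0.5 / √(9 + 0.125) = 0.166. Neither f nor SD is in the protocol, so these are assumed ranges:

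| SD | f = 0.25 | f = 0.5 | f = 1 |
|---|---|---|---|
| 3 | 0.083 | 0.166 | 0.333 |
| 5 | 0.050 | 0.100 | 0.200 |
| 10 | 0.025 | 0.050 | 0.100 |

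**3. What matching does.** A simulation gave both arms the same negative binomial distribution of true counts (400,000 per arm), added one code to a share f of DEX+ patients, and matched 1:1 exactly on the recorded count. Recorded counts are then equal. The true counts (DEX+ minus referent) are not:

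| Mean / SD | f | Difference in true count | Standardized difference |
|---|---|---|---|
| 5 / 3 | 0.25 | −0.248 | −0.084 |
| 5 / 3 | 0.5 | −0.493 | −0.169 |
| 5 / 3 | 1 | −1.000 | −0.354 |
| 10 / 5 | 0.25 | −0.248 | −0.050 |
| 10 / 5 | 0.5 | −0.498 | −0.101 |
| 10 / 5 | 1 | −1.000 | −0.208 |
| 20 / 10 | 0.25 | −0.251 | −0.025 |
| 20 / 10 | 0.5 | −0.498 | −0.050 |
| 20 / 10 | 1 | −1.000 | −0.102 |

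Matched DEX+ patients have about f fewer true codes than their referents, while the recorded balance looks perfect. Exact matching on this one variable is the clearest case. In a PS with many covariates the count is one contributor, so the transfer may be weaker.

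**The case against.** **Table 3 lists candidates only.** Sections V.F and VI.A allow a subset, refitting and removal. This stands: the protocol does not say that the PS will contain the count. It does not dispose of the point, because row 3 of Table 4 checks balance of all potential confounders, including those dropped from the model, and section VI.C lets an imbalanced variable enter the Cox model.

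**Code lists belong in a specification.** Section V says that further measure definitions are available on request, so an exclusion may exist there. That is possible. But the window through Day T is stated in the protocol, and followed as written it admits the exposure code.

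**Most inpatient drug data come from charge-code text.** This stands and limits the size. The share f is unknown and may be well below 1. A reader might infer that an SD of 10 or less is enough to breach the 0.10 limit; that is true only if every DEX+ patient gains a code. The limit is also applied after matching, so a pre-matching shift does not show that the criterion fails.

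**Department codes do not define exposure.** This stands. A dexamethasone charge inflates that count only if it brings a department not otherwise recorded for the patient, which the documents do not show.

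**Severity is controlled elsewhere.** Risk-set sampling matches on mWHO category, time since admission, age, sex and comorbidity score. ICU care, ARDS, shock and organ support are further candidates. What one extra code adds about prognosis given these is unknown, and probably little.

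**Conclusion.** The point holds in a limited form. As written, the candidate procedure-code count can contain the exposure in DEX+ patients but not in CSI- referents, which is the primary comparison, and largely not in DEX- referents. The ASD check cannot detect this once the recorded count has been matched.

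Under the assumed ranges (f 0.25 to 1, SD 3 to 10), the spurious ASD before matching runs from about 0.03 to 0.33, that is, from negligible to above the protocol's limit. Section V.C.2 says that more than 80% of initiators start within 1 or 2 days of hospitalization. Windows are therefore mostly short, but the distribution of the counts is not reported.

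A reader might infer that the PS definitely embeds treatment, or that the DEX effect is materially biased. The documents support neither: inclusion is not settled, the share recorded by procedure code is not given, and no effect on the hazard ratio has been shown. The direction, in favour of DEX, depends on higher counts marking sicker patients. This is a worthwhile clarification and not a threat to the design.

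**What to change.** Keep the Day 0 to Day T window. Add one sentence to Table 3: codes for dexamethasone and the other corticosteroids of interest, and for giving them, do not enter the procedure-code count, and a department recorded only through such a charge does not enter the department-code count. Apply the same derivation in the PS model, the balance table and any adjusted Cox model. Removing all corticosteroids of interest, and not dexamethasone alone, also keeps the DEX- and MPRED+ comparisons even.

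The cost is a filter on two derived variables, using code lists that the exposure and washout definitions already require. It can be done in the diagnostic phase, before any treatment effect is estimated.

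Do not end the counts at Day T−1 instead. For patients who start on Day 0 that leaves no window; if the rule covers only later starters, it leaves the artefact in the Day 0 group. It would also discard genuine index-day care that Table 3 sets out to capture.

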**G. Statistical Software**

Primary analyses will be conducted using the Aetion Evidence Platform® (2020) software for real-world data analysis, which has been validated for a range of studies *[Wang 2016]*. Supplemental analyses and additional plots will be created using R 4.0.3 (2020-10-10).

**VI. STATISTICAL METHODS**

**A. Propensity score model fitting**

Propensity score (PS) matching will be used to control for confounding by identifying referent patients who are comparable to DEX+ patients with respect to several covariates identified *a*

*priori* for their potential to introduce confounding. Multivariable logistic regression will be used to estimate the propensity to initiate DEX+ versus each referent group (CSI-; DEX-; MPRED+), based on main effects of the independent covariates without interaction terms. PS model coefficients will be estimated using the overall study cohort. Appropriate referent groups will be identified using nearest neighbor matching with a caliper width of  $\pm 1\%$ . Referent groups for subgroup analyses will be identified using the overall PS model [Wang 2018, Strategy A].

Model fit and performance will be evaluated using the criteria outlined in Table 4. The PS model for the primary objective will be deemed acceptable if all the criteria described in Table 4 are achieved. We will further attempt to satisfy all criteria for secondary objectives, but strategies such as covariate adjustment to control for residual imbalance may be used in the event that some criteria are not satisfied.

As a secondary modeling strategy, we may consider estimating PS model coefficients within each subgroup and pooling subgroup matches to form the overall cohort. This modeling strategy may be used for the final analysis if diagnostic criteria outlined in Table 4 are improved [Wang 2018, Strategy C].

In our primary variable selection strategy, we will 1) define a list of potential covariates *a priori* as described in Section V.F; 2) specify one or several models using all or a manually selected subset of the covariates; 3) assess model diagnostics, including but not limited to diagnostic assessments described in Table 4; and 4) refit models in response to diagnostic results providing information about over-fitting, positivity violations, or covariate instability. Possible strategies for improving model fits may include collapsing sparse or collinear variables into composite variables where appropriate, or removing variables from the model if covariate balance is maintained between DEX+ and referent groups. We may also consider automated variable selection strategies such as HDPS or LASSO if they improve model fits relative to manual variable selection.

**B. Diagnostic phase and checklist**

The diagnostic phase checklist developed for this study is shown in Table 4 below. Upon each data update, the diagnostic results will be executed and discussed with the FDA RCA team until there is consensus that we have satisfied the necessary criteria for the primary objective in the overall cohort to progress to the *Inferential Phase*. Sample size calculations are part of the iterative cycle of the *Diagnostic Phase* rather than fully completed in advance to allow consideration of new study findings (in addition to the RECOVERY trial [RECOVERY 2020]) that impact the assumptions underlying the sample size calculations. Treatment effects will not be estimated during the *Diagnostic Phase*. All treatment effects will be examined during the *Inferential Phase* after the data is locked and propensity score models are finalized.

Table 4: Diagnostic checklist to complete prior to progression to the inferential phase

#	Diagnostic	Description	✓
1	Confirm adequate sample size	Adequate sample size will be defined as the minimum sample size required to achieve 80% power using a 2-sided 95% confidence interval (0.05- alpha ) assuming a hazard ratio of 0.8 and the baseline risk of 28-day mortality in the primary referent CSI- group estimated as the risk in the RSS-matched CSI-group prior to PS matching (since the baseline risk is otherwise unknown in the	

		US patients hospitalized for COVID-19). Further confirm which subgroups of interest achieved minimum sample size for formal hypothesis testing.	
2	Confirm positivity of variables	PS distributions will be visually inspected, and overlap in all areas of the PS distributions will be confirmed.	
3	Confirm baseline confounder balance	We will confirm that the distributions of all potential confounders are balanced for DEX+ vs. referent. Covariate balance will be defined as absolute standardized differences (ASDs) $\leq 0.10$ [Austin 2009].  Although variables with balance prior to PS matching may be removed from the PS model, balance of these variables will still be confirmed after PS matching.  If there is a variable with a small residual imbalance ( $0.10 \leq ASD \leq 0.20$ ), balance may be deemed acceptable if the variable does not predict the outcome among the referent group (defined as an ASD $< 0.10$ when comparing the risk of the outcome in those with the variable vs. those without it). Evaluation of imbalance in outcome prediction will only be conducted once at the end of the diagnostic phase if all other diagnostic criteria are met.	
4	Confirm models are not overfit	We will confirm that all models contain approximately 12 exposed subjects or more per covariate	

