## **B. Randomized Evaluation of COVID-19 Therapy (RECOVERY): Efficacy of dexamethasone**

The RECOVERY trial, which first reported preliminary results on June 22, 2020, was an open-label, 1:2 randomized controlled trial of 6,425 patients randomized to either 6 mg of DEX daily for 10 days (n = 2,104) or usual care (n = 4,321). Overall, 22.9% of patients assigned to the DEX group died within 28 days of randomization vs. 25.7% of the control arm (rate ratio [RR] of 0.83, 95% CI [0.75, 0.93]). The difference in survival between the two groups varied noticeably when stratified by baseline COVID-19 severity level. While the incidence of death was lower in the DEX group, compared to the usual care group, among patients receiving IMV (RR: 0.64, 95% CI [0.51, 0.81]) and among those receiving supplemental O2 therapy but not IMV (RR: 0.82, 95% CI [0.72, 0.94]), there was no discernable difference among patients who were not receiving any supplemental O2 (RR: 1.19, 95% CI [0.91 to 1.55]) [*RECOVERY 2020*].

The effectiveness of DEX in preventing death among moderate to severe COVID-19 patients has not yet been confirmed or established in routine care, yet DEX utilization has substantially increased in the US since June 2020 [*Action 2021*]. Thus, to evaluate the effectiveness of DEX in preventing death under routine use in a timely manner, we sought to conduct an observational cohort study using US-based real-world data (RWD).

[figure not shown]
In one of the explorations conducted prior to the finalization of this protocol [see *Appendix A.2. Exploration 2*], we compared the distribution of key patient characteristics between a version of our hospitalized US-based RWD study cohort to those reported for the hospitalized UK-based patients randomized in the RECOVERY trial. The RECOVERY trial was a large, pragmatic randomized trial that simplified the data collection process in an effort to minimize the already heavy burden of the pandemic on frontline workers. Exploration of baseline clinical differences between the real-world study and trial populations was therefore limited by the degree of available information for the trial patients. However, among the available RECOVERY trial data, we identified important clinical and demographic differences in the trial population versus this study's populations at baseline.

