**C. Inferential phase**

The *Inferential Phase* begins after all diagnostic criteria are satisfied or the protocol is publicly posted, whichever is later. To prevent changes to the underlying patient or event-level data from occurring when new data are available, the data cut will be locked at the start of the *Inferential Phase*.

For the primary outcome of 28-day mortality, the following will be reported in the overall cohort and within each subgroup of interest before PS matching and after PS matching:

- Rates reported per 1,000 person-days, overall and for each subgroup.
- Hazard ratios (HR) and corresponding 95% CIs for the effect of DEX+ compared to each referent (CSI-; DEX-; MPRED+) overall and for each subgroup using PS-matched cohorts. If residual imbalance ( $0.10 \leq ASD \leq 0.15$ ) remains after PS matching, Cox proportional hazard models may be specified to adjust for any imbalanced confounders. Otherwise, HRs will be unadjusted.

In subgroups that do not achieve the minimum sample size requirements, results will be presented in the context of an estimation framework rather than a formal hypothesis testing framework, and findings should be interpreted with caution.

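### The minimum sample size that admits severity subgroups to formal testing is defined only from the primary CSI- group's death risk, so a lower-risk subgroup could qualify with less than 80% power

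*Protocol*

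**What the plan says.** Protocol section VI.B, Table 4 row 1, defines adequate size as the number of patients needed for "80% power using a 2-sided 95% confidence interval", "assuming a hazard ratio of 0.8 and the baseline risk of 28-day mortality in the primary referent CSI- group". That risk is "estimated as the risk in the RSS-matched CSI-group prior to PS matching". The row then adds: "Further confirm which subgroups of interest achieved minimum sample size for formal hypothesis testing".

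Section VI.C attaches the consequence: "In subgroups that do not achieve the minimum sample size requirements, results will be presented in the context of an estimation framework", with a caution on interpretation.

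The key subgroups (section III and Table 1) are no O2, O2/NIV, IMV and the O2/NIV/IMV composite, each compared with CSI-, DEX- and MPRED+. Row 1 names a baseline risk for one referent group only, CSI-, and none for any severity level. Section V.C.2 leaves the matching ratio open between 1:1 and 1:4 for the two non-user comparisons.

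**The concern.** A required number of patients is a stand-in for a required number of deaths, and the conversion holds only at the risk used to make it. These subgroups are defined by severity, so there is good reason to expect their death risks to differ from the overall risk. Reusing one number then gives a lower-risk subgroup too few deaths and asks more patients than necessary of a higher-risk one.

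The label attached to key results is at stake. A subgroup that passes is reported as a formal test and escapes the caution in section VI.C. No O2 is the group in which section II.B reports no discernible benefit in RECOVERY (rate ratio 1.19, 0.91 to 1.55), and it was the largest severity group in the early matched cohort (Appendix A, Table A.3: 59.7%). It is therefore a likely group to pass a patient-count rule, and a null result there could be over-read as an adequately powered test.

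**Working it through.** The protocol prints no required number of patients, deaths or achieved power, so there is no figure of its own to reproduce.

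**1. Deaths required at hazard ratio 0.8** (Schoenfeld; two-sided 0.05, 80% power, DEX+ share p):

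D = (1.96 + 0.8416)² / [p(1 − p)(ln 0.8)²] = 7.849 / [p(1 − p) × 0.04979]

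- 1:1 (p = 1/2): 631 (Freedman's formula: 636)
- 1:2: 710
- 1:3: 841
- 1:4: 986

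**2. Conversion to patients at 1:1.** With referent risk q and DEX+ risk 1 − (1 − q)^0.8, total N = D / mean risk, ignoring censoring at discharge. The overall CSI- risk is not printed, so these values of q are assumptions; the highest is the RECOVERY control-arm risk in section II.B.

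| Overall CSI- risk | Minimum total N |
|---|---|
| 10% | 6,974 |
| 15% | 4,638 |
| 20% | 3,470 |
| 25.7% | 2,692 |

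**3. Power of a subgroup that just reaches that N.** Power = Φ(√(deaths × p(1 − p)) × |ln 0.8| − 1.96). It depends almost only on the subgroup's risk relative to overall, and hardly changes between 1:1 and 1:4.

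| Subgroup risk ÷ overall risk | Power |
|---|---|
| 0.5 | 51% |
| 0.6 | 58% |
| 0.7 | 65% |
| 0.8 | 71% |
| 1.0 | 80% |
| 1.5 | 93% |
| 2.0 | 98% |

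Example with an assumed overall risk of 15%: a subgroup at 7.5% with 4,638 patients expects about 314 deaths, hence 51% power; it would need 9,310 patients. A subgroup at 30% would need only 2,301.

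**4. Approximate relative risk of no O2, from printed figures.** Section II.B gives RECOVERY's rate-ratio intervals by severity, and Table A.3 gives the arm sizes. With SE = ln(upper/lower)/(2 × 1.96), implied deaths are about 1/[SE² p(1 − p)].

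| RECOVERY group | Interval | Arms | SE | Implied deaths | Implied risk |
|---|---|---|---|---|---|
| No O2 | 0.91–1.55 | 501 / 1,034 | 0.136 | 246 | 16% |
| O2 | 0.72–0.94 | 1,279 / 2,604 | 0.068 | 979 | 25% |
| IMV | 0.51–0.81 | 324 / 683 | 0.118 | 329 | 33% |

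These average 24.2% over the 6,425 patients. Directly from section II.B, (0.229 × 2,104 + 0.257 × 4,321)/6,425 = 24.8%, so the approximation is serviceable.

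- Against RECOVERY's overall risk, no O2 stands at 0.65 to 0.66: power about 62% to 63%.
- Reweighted to the matched severity counts in Table A.3 (1,098, 592 and 62 per arm), the overall risk is 19.7% and no O2 stands at 0.81: power about 71%.

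**5. IMV at the printed sizes.** Table A.3 shows 62 per arm; Figure A.5 refers to 834 IMV patients. Taking 834 as a 1:1 total, power is 39% at 30% risk, 50% at 40% and 59% at 50%. It reaches 80% only at a risk of about 80%. IMV therefore misses its own requirement as well as the overall one.

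**The case against.** The best defence is that the protocol never says the overall risk must be reused for subgroups. Adequate size is defined by 80% power, section VI.C speaks of requirements in the plural, and section VI.B makes sample size calculation iterative, with review alongside the FDA team at each data update. The subgroup inputs could then be detail left for later. Part of this stands: reuse of the overall risk is the literal reading, not an express instruction. But row 1 goes beyond silence. It defines one minimum and, in the next sentence, uses that term to admit subgroups to testing. If subgroup-specific minima are intended, the same edit is needed to say so.

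It is also fair that hazard ratios and 95% intervals are reported for every subgroup whatever the outcome, and that progression to the Inferential Phase depends on the overall cohort only. That limits the consequence to framing.

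Three stronger readings are tempting, and the documents do not support them:

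- **That no O2 would be tested at very low power, below 40%.** This needs a no-O2 risk of about a third of overall. No death risk by severity is printed, and the RECOVERY figures point to 62% to 71%. A subgroup forming more than half the cohort also pulls the overall risk towards its own.
- **That IMV is denied a test it deserves.** At the printed sizes it falls short under either rule. The rule would bite only if later data updates brought IMV between its own requirement and the overall one.
- **That section II.B shows death risk varying by severity.** The sentence "The difference in survival between the two groups varied noticeably when stratified by baseline COVID-19 severity level" concerns the treatment effect, not the baseline risk.

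**Conclusion.** The point holds as a rule that misfires when followed as written. The direction is certain: any subgroup whose risk is below the overall CSI- risk and that just meets the single minimum has less than the stated 80% power at hazard ratio 0.8. The size is moderate and approximate. For no O2 it is about 62% to 71% power if its risk is 0.65 to 0.8 times overall, which rests on risks backed out from RECOVERY and on their transfer to this US cohort. It is about 51% if the risk is half of overall, which is purely an assumption. The converse for higher-risk subgroups is correct in principle but has no effect at the printed IMV sizes. The primary objective in the overall cohort is untouched; only the status given to key subgroup results is affected.

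**What to change.** In Table 4 row 1, state that each subgroup and comparator is judged against its own minimum number of patients for 80% power at hazard ratio 0.8, computed from that subgroup's own RSS-matched referent-group 28-day risk and the chosen matching ratio. This is equivalent to 631 expected deaths at 1:1, 710 at 1:2, 841 at 1:3 and 986 at 1:4. Make the sentence on subgroups in section VI.C refer to these minima.

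Add that neither DEX+ deaths nor deaths pooled over both arms are viewed for this purpose in the Diagnostic Phase. A rule based on observed pooled deaths looks simpler, but set beside a known referent risk it would let the DEX+ risk be approximated, against the commitments in sections II.C and VI.B. Referent-group risk is the kind of information row 1 already uses.

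The cost is wording only, before the Inferential Phase. The downside is that no O2 may move to the estimation framework.
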